**Secondary Analyses (week 76)**

Individuals are allowed to stop the intervention after week 24, as such the mean group and individual level effects may be quite different at week 76. Consequently we analyse week 76 data separately from the earlier weeks. All efficacy outcomes (see pg 4) will be analysed using linear regression models. The FinAS cohort will be used. Missing baseline covariate data are assumed to be infrequent and imputed using cohort means.

Estimates and 95% CIs will be reported per group for all assessments (restricted maximum likelihood estimates), however pairwise comparisons will only be assessed if the overall effect of Group is significant (likelihood ratio test). Significance will be considered at  $p < 0.05$  (two-sided) with no adjustment for multiple testing and conclusions interpreted as exploratory.

Cohort: FinAS

Model:  $Y \sim \text{Group} + \text{Sex (M v F)} + \text{AUSDRISK} + Y0$

- Y = Week 76 assessment
- Y0 = Baseline assessment
- Group: CR vs IF vs SC.
- AUSDRISK and Y0 included as a continuous linear variables.

Visual inspection of residual and random effect distributions will be undertaken. If residual distributions appear not satisfactory then log transformations will be applied and if still not satisfactory GLMMs will be considered with different error distributions.

	Group p-value	Visit (wk 76)	
		Est [95%CI]	p-value*
Outcome 1			
CR v SC	PP	XX [YY, ZZ]	PP
IF v SC		XX [YY, ZZ]	PP
IF v CR		XX [YY, ZZ]	PP
Outcome 2			
CR v SC	PP	XX [YY, ZZ]	PP
IF v SC		XX [YY, ZZ]	PP
IF v CR		XX [YY, ZZ]	PP

\*Only reported if the overall Group test is significant ( $p < 0.05$ ).

**Bayesian Joint Secondary Analysis of Postprandial Glucose and HbA1c**

The posterior probabilities of the between group difference in HbA1c for CR vs IF, and for SC vs IF+CR combined will be calculated using a sceptical bivariate Gaussian normal prior. This prior will be mean centred and with covariance

$$\Sigma = \begin{bmatrix} 0.14 & 0.08115171 \\ 0.08115171 & 0.096 \end{bmatrix},$$

corresponding to a correlation of 0.7 and variance of 0.14 for HbA1c and 0.15 for post-prandial glucose AUC. (Note there is an error in the protocol paper Teong et al 2020 where the post-prandial glucose variance was reported as 1.5 across standardized mean differences in historical studies. Converting to units of mmol/h we assume a SD of 0.8.)

We assume that observations from individuals in this study are exchangeable under the prior.

This analysis uses the PAS cohort.

To mimic the study design, the posteriors will be calculated in two stages: (A) initially including individuals used in the interim analysis and (B) then the subsequently randomized individuals. Each stage calculates the likelihood for the between group mean difference in the within-individual change from baseline values, assumed to be normally distributed with known variance. The posterior from the first stage is included as the prior for the second stage.

Reported will be

1. The mean and co-variance matrix for the posterior distribution
2. The probability that the change in HbA1c for
  - a. IF vs CR is less than -0.3%, and vice versa.
  - b. IF+CR vs SC is less than -0.3%.
3. The probability that the change in postprandial glucose AUC for
  - a. IF vs CR is less than -0.4 mmol/h and vice versa.
  - b. IF+CR vs SC is less than -0.4 mmol/h.
4. The joint probability that for IF+CR vs SC
  - a. Either HbA1c is less than -0.3% or postprandial glucose AUC is less than -0.4 mmol/h.
  - b. Both HbA1c is less than -0.3% and postprandial glucose AUC is less than -0.4 mmol/h.

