### **Study Design Change**

*Changes made prior to 2nd Interim Analysis – accepted by the DMC. Primary investigator (LH) was blinded to the results of interim analysis 1.*

Given the interruption due to COVID-19 it was considered ill advised to continue accrual. Regarding study design, the study team chose to consider change in glucose control as the single primary outcome and change in HbA1c as a secondary outcome, with no further interim analyses (for efficacy).

The original design had HbA1c and glucose AUC as dual primary endpoints and envisaged 3 interim analyses (at N/6, N/3 and N/2), with a multiple testing adjusted two-sided alpha=0.05 (ie two-sided alpha=0.025 for each endpoint). Assuming 25% attrition a N=260 would provide at least 80% power for the HbA1c endpoint and >90% power for the glucose AUC endpoint.

With this new design and assuming 25% attrition and a pre-post correlation of 0.4, then a sample size of N=208 (83:83:42 in the three arms) provides at least 85% power to detect a mean difference of 0.4 mmol/h (SD=0.8) in glucose AUC between the two active interventions (two-sided alpha=0.04999992).

*At the first interim analysis (N/6) negligible alpha was spent. Assuming trial could stop for a Type I error in either outcome 6.3e-07 was spent (gsDesign).*

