**Primary Outcome Comparison**

Objective: Week 24 post-prandial glucose AUC for CR and IF groups.

Cohort: PAS

Linear regression model:  $Y \sim \text{Group (CR v IF)} + \text{Sex (M v F)} + \text{AUSDRISK} + Y0$

- $Y$  = Post prandial glucose;  $Y0$  = Baseline post prandial glucose assessment
- AUSDRISK and  $Y0$  included as a continuous linear variables.
- Missing baseline covariate data are assumed to be infrequent and imputed using cohort means.
- Significance is one-sided  $p < 0.04999992$  (two-sided).

	Est [95%CI]	p-value
IF v CR	XX [YY, ZZ]	PP

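### The Bayesian analysis uses unadjusted change from baseline, unlike every efficacy regression in the SAP, and so discards precision: the glucose AUC likelihood variance is 43% larger at the plan's correlation of 0.4 (equal SDs assumed)

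*SAP*

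**What the plan says.** The Bayesian section of the SAP defines the likelihood as follows: "Each stage calculates the likelihood for the between group mean difference in the within-individual change from baseline values". These differences are "assumed to be normally distributed with known variance", but neither a value nor a source for that variance is given, and no covariate is named. On the population it says "This analysis uses the PAS cohort", which is also the population of the primary analysis.

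The other efficacy models are built differently. Primary Outcome Comparison regresses week 24 glucose AUC on group, sex, AUSDRISK and Y0, where Y0 is the "Baseline post prandial glucose assessment". Both week 24 secondary models, the week 76 model ("Y0 = Baseline assessment") and the model for the two-weekly weights carry the same three adjustment terms.

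Study Design Change sizes the trial "assuming 25% attrition and a pre-post correlation of 0.4" and states that N=208 (83:83:42) "provides at least 85% power to detect a mean difference of 0.4 mmol/h (SD=0.8) in glucose AUC" between the two active arms.

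**The concern.** A change score in effect fixes the coefficient on baseline at 1. Regression estimates it, and with equal SDs and a correlation of 0.4 the estimate should be near 0.4. With a correlation this low, subtracting the whole baseline value adds more noise than it removes: the per-person variance is 1.20 SD², against 1.00 SD² if baseline were ignored.

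This matters in two ways. The posterior covariance and the probabilities at -0.4 mmol/h and -0.3% would be less precise than the collected data allow, and the sceptical prior would get more weight. In addition, the IF v CR difference in glucose AUC would be estimated in the same people by two different estimators, one in the primary analysis and one here, so the two could disagree for no scientific reason.

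**Working it through.** **Inputs.** From Study Design Change: difference 0.4 mmol/h, SD 0.8, correlation ρ = 0.4, two-sided alpha 0.04999992, 83 per active arm and 42 in SC, 25% attrition. That leaves 83 × 0.75 = 62.25, taken as 62 per active arm, and about 31 in SC. From the Bayesian section: prior variance 0.096 for the AUC difference. Assumption: equal SDs at baseline and week 24, relaxed below.

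**The plan's power figure.** Noncentral t, 62 per arm:

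| Per-person SD | Value | Power |
|---|---|---|
| Baseline-adjusted, 0.8·√(1−0.4²) | 0.733 | 85.4% |
| Baseline ignored, or 0.8 read as the SD of change and analysed unadjusted | 0.800 | 78.9% |
| Change score, 0.8·√(2(1−0.4)) | 0.876 | 71.3% |

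Reading 0.8 as the SD of change and then adjusting for baseline gives about 91%. Only the first row lands on the stated figure of at least 85%, so the trial was sized on the baseline-adjusted variance.

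**Likelihood variance, IF v CR.**
- Change: 0.64 × 1.20 × 2/62 = 0.02477 (SE 0.157)
- Adjusted: 0.64 × 0.84 × 2/62 = 0.01734 (SE 0.132)
- Ratio: 1.20/0.84 = 2/(1+ρ) = 1.429, i.e. variance +43%; SE ratio √1.429 = 1.195, about +20%

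**Unequal SDs.** With q = baseline SD / week 24 SD, the ratio is (1 + q² − 0.8q)/0.84. It is 1.19 at q = 0.8 and 1.76 at q = 1.2. It reaches 1 only at q = 0.4 and is never below 1.

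**Posterior for glucose AUC alone, IF v CR.** Posterior variance = 1/(1/0.096 + 1/V); weight on the data = posterior variance / V.
- Change: variance 0.01969, SD 0.140, weight 0.795
- Adjusted: variance 0.01469, SD 0.121, weight 0.847
- Variance ratio: 1.34

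| Observed difference | P(< −0.4), change | P(< −0.4), adjusted |
|---|---|---|
| −0.6 | 0.71 | 0.81 |
| −0.4 | 0.28 | 0.31 |
| −0.3 | 0.12 | 0.11 |
| −0.2 | 0.04 | 0.03 |

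If 0.8 were itself plugged in as the known SD of change, the variance would be 0.64 × 2/62 = 0.0206 and the probability at −0.6 would be 0.76.

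**Bivariate check.** This uses the plan's prior matrix. The SAP gives no HbA1c SD or pre-post correlation, so these are assumed: HbA1c SD 0.3 or 0.5%, HbA1c correlation 0.4 to 0.8, HbA1c–AUC error correlation 0.3 or 0.6.
- AUC posterior variance ratio: 1.29–1.32 for IF v CR, 1.27–1.31 for IF+CR v SC
- P(both thresholds met), IF+CR v SC, change v adjusted: 0.15–0.17 v 0.17–0.19 at observed (−0.3%, −0.4), and 0.51–0.65 v 0.63–0.75 at (−0.4%, −0.6)

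For HbA1c's own likelihood, 2/(1+ρ) gives +33% at an assumed correlation of 0.5, +25% at 0.6 and +11% at 0.8.

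**Disagreement with the primary estimate.** Under the same assumptions, the two IF v CR estimates differ from each other with SD √(0.02477 − 0.01734) = 0.086 mmol/h.

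**The case against.** The best defence is that this is a valid method, openly stated. The change score is unbiased, the reported probabilities are worded in terms of change, no decision rule depends on them, and nothing in the SAP says the Bayesian likelihood must follow the primary model. All of that is true, and it limits the point to efficiency and consistency. It does not explain why this one analysis should forgo an adjustment that every other efficacy model makes. Regressing change on group and baseline gives the same group coefficient as regressing the week 24 value on them, so even the wording about change could stay.

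The size can also be challenged. The 43% needs equal SDs, the known variance is unstated, and HbA1c has no stated correlation. This stands: 43% belongs to glucose AUC under the stated assumption, and the HbA1c and bivariate figures are ranges over assumed inputs. The direction holds throughout the SD range examined. Near the design difference the probabilities move little, and for small effects the direction reverses.

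Finally, adjustment has a cost. In a simulation with four covariates fitted separately in each stage, with 13–17 per active arm in stage A and no added prognostic value from the other covariates, the advantage falls from 43% to about 35% (39% in a single stage). Most of the gain remains. It is also fair that adjusting for both baselines would not reproduce the primary estimator exactly, since that model uses only the outcome's own baseline; the two would nevertheless be far closer than they are now.

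**Conclusion.** The concern holds. The Bayesian analysis departs without explanation from the adjustment used in all the efficacy regressions and loses precision by doing so. For glucose AUC the likelihood variance is 43% larger (SE 20%) at the plan's correlation of 0.4 with equal SDs, and 19% to 76% larger for a baseline to week 24 SD ratio of 0.8 to 1.2. The posterior variance for IF v CR is 34% larger taking glucose alone, and 29% to 32% larger under the bivariate prior with the assumed HbA1c inputs. The figures count baseline adjustment only; the SAP gives nothing from which to size any gain from sex and AUSDRISK. There is no bias and no effect on the primary test. It should be changed because the improvement uses data already collected.

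**What to change.** Build the bivariate normal likelihood from the baseline-adjusted week 24 group differences and their covariance, taken from a regression of HbA1c and glucose AUC on group, sex, AUSDRISK and both baselines. State that the known variance is the residual covariance from that regression, pooled over both stages, and say whether the covariate slopes are also pooled or fitted per stage. Keep the prior, thresholds and reported quantities. The change-score posterior can stay as a sensitivity analysis.

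One clarification in the same section: stage B is described as "B) then the subsequently randomized individuals". Define it as all members of the PAS not in stage A, so that the two stages together cover the whole set.

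The cost is SAP wording and minor code, with no new data. Under randomisation both estimators target the same between-group difference, so the prior and thresholds still apply.

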**Weekly weight assessments**

There are non-fasting weight assessments reported every 2 weeks. These data will be analysed similarly to the other secondary analyses, with however piecewise linear effects assumed for the interventions over two time periods: weeks 1-24 and 25-76. The model will include random intercepts and slopes for individuals. Again pairwise comparisons will only be assessed if the interaction tests Time1 x Group and Time2 x Group are significant (likelihood ratio test).

Models:  $Y \sim (\text{Time1} + \text{Time2}) + \text{Group} + (\text{Time1} + \text{Time2}) \times \text{Group} + \text{Sex} + \text{AUSDRISK} + Y_0 + (1 + \text{Time1} + \text{Time2} | \text{ID})$

- Time1 = Week number (1 to 76).
- Time2 = Zero for weeks 1 to 24, and week number minus 24 for weeks 25+.

Int. p-value	Group	Estimate	Coef [95%CI]	p-value*
PP	SC	Slope: wks 1-24	XX [YY, ZZ]	PP
PP	SC	Slope change: wk 25-76	XX [YY, ZZ]	PP
	CR	Slope: wk 1-24	XX [YY, ZZ]	PP
	CR	Slope change: wk 25-76	XX [YY, ZZ]	PP
	IF	Slope: wk 1-24	XX [YY, ZZ]	PP
	IF	Slope change: wk 25-76	XX [YY, ZZ]	PP
	CR v SC	Comparison: slope	XX [YY, ZZ]	PP
	CR v SC	Comparison: slope change	XX [YY, ZZ]	PP
	IF v SC	Comparison: slope	XX [YY, ZZ]	PP
	IF v SC	Comparison: slope change	XX [YY, ZZ]	PP
	IF v CR	Comparison: slope	XX [YY, ZZ]	PP
	IF v CR	Comparison: slope change	XX [YY, ZZ]	PP

\*Only reported if the respective interaction p-values for slope and slope-change are significant.

*Adverse Event Analyses*

It is assumed that the number of AEs will be low, and as such Fisher exact tests will be used to compare: CR vs IF vs SC (ie two degrees of freedom) when the number of individuals with an event is at least 4.
